#### **IV. Regulatory & Continuing Review Completion Plan**

##### Step-by-Step Communication Plan

The primary additional contact (department regulatory officer) listed on the IRB study team will be responsible for initiating the CR, when the CR notification is automatically sent by the IRB system 90 days prior to study expiration. Department contact will email study team notifying them that CR has been opened and set a timeline that is 8 weeks prior to study expiration for CR submission.

A study team member, in the key personnel, co-investigator, or principal investigator role, will be asked to complete the details of the CR to include participant numbers, status of project, or any events that require reporting. This ensures that all “engaged” study team members participate in the CR and may serve in completing the CR.

The department additional contact will follow-up with the study team via email 2x before setting up a meeting with PI to complete the CR.

The PI will submit the ready CR at least 48hrs prior to the 8 week deadline.

The 8 week deadline insures that at least 4 IRB board meetings occur prior to study expiration to account for request for modifications, delays from IRB, or other unforeseen circumstances that may cause a lapse in study.

TITLE: Prospective, Single-Blinded, Randomized-Controlled Trial Comparing the Performance Profiles of Two Non-Cross-Linked Porcine Dermal Matrices in Abdominal Wall Reconstruction

Statistical Analysis
Document Date: February 18, 2025
NCT # NCT02228889

Principal investigator: [name], FACS (Professor of Plastic Surgery)

Comparative Outcomes of Stratdice vs. XenMatrix in Complex Abdominal Wall Reconstruction, PI: [name]

[name], MS

Updated: 18 February, 2025

Contents

Statistical Analysis Plan	2
Overview	2
Statistical Analysis	2
Descriptive Analysis	2
Primary Outcome Analysis	2
Statistical and Study Design Considerations	2
Rationale for Combining RCT and Observational Study Data	2
Choice of Statistical Methods	2
Methodology implementation notes	3
Additional comments	3
References	3
Additional Exclusion Criteria	4
Tables	5
Baseline Characteristics	5
Surgical Characteristics	7
6-week Outcomes	8
Results	10
Executive Summary	10
Unadjusted Random Effects Meta-Analysis (Simple Logistic Regression):	10
Adjusted Random Effects Meta-Analysis (Multivariable Logistic Regression):	10
Note	10
Random Effects Meta-Analysis: Simple Logistic Regression	11
Forest Plot: Log Odds Scale	11
Forest Plot: Odds Scale	12
Random Effects Meta-Analysis: Multivariable logistic regression	13
Log Odds Scale	13
Odds Scale	14
FAQ	14
R Session info	17

Statistical Analysis Plan

Overview

This study aims to evaluate the effect of using XenMatrix or Strattice mesh on the occurrence of surgical site occurrences (SSO) within six weeks post-surgery. Patient-level data were drawn from two sources:

- A single-site randomized controlled trial (RCT), and
- A single-site observational study.

These datasets were combined using a random-effects meta-analysis to generate an overall estimate of the treatment effect of mesh type on the risk of SSO.

Statistical Analysis

Descriptive Analysis

An unadjusted analysis comparing mesh was performed.

- Baseline Characteristics: Descriptive statistics (e.g., means or medians for continuous data, counts and proportions for categorical data) were generated for both the RCT and observational cohorts.
- Group Comparisons:
 - Continuous variables were compared using the Kruskal–Wallis test.
 - Categorical variables were compared using Pearson's Chi-square test.

Primary Outcome Analysis

SSO within 6 weeks was analyzed using logistic regression. Separate logistic regression models were fit for the RCT and for the observational cohort, with mesh type (XenMatrix vs. Strattice) as the primary predictor. Simple logistic regression and multivariable logistic regression was used for each study type (RCT and observational). Both models were adjusted by hernia width, CDC wound class, immunosuppression, and recurrent hernia to account for potential confounding in the observational group. Covariates were selected based on evidence in the literature as well as potential imbalance. The final number of covariates was limited to avoid model overfitting.

Confounders:

- Hernia width
- Wound class
- Immunosuppression
- Recurrent hernia

After obtaining separate estimates from the RCT and observational cohort, a random-effects meta-analysis was performed to derive a combined estimate. A combined estimate for the log odds ratio was calculated using inverse variance weighting and a restricted maximum likelihood estimator. Between-study heterogeneity was assessed by the I^2 measure.

Forest plots and summary tables for the log odds ratio and odds ratio were generated to summarize results.

Statistical and Study Design Considerations

Rationale for Combining RCT and Observational Study Data

- RCT was terminated early for difficulties with enrollment, resulting in very imbalanced group sizes.
- While some guidelines caution against combining observational studies with RCTs in a single meta-analysis due to methodological differences [2], other sources emphasize that in many situations, the benefits of incorporating all available evidence can outweigh the drawbacks, provided proper methods are used [2, 3]
- [3] proves a framework for synthesis of non-randomized and randomized studies.
 - In this study, the observational data come from the same single site as the RCT and are not subject to publication bias.

Choice of Statistical Methods

- Frequentist methods were chosen for broader audience familiarity. Although Bayesian multi-level models are an option, they can be sensitive to prior specification, and the intended audience may be less familiar with them.
- There are not enough events to perform analysis for other outcomes.
- Propensity score matching was not used because it can substantially reduce the sample size (i.e., discarding unmatched patients).

- Statistical methods chosen to maximize data (Propensity score matching methods throw away data). Methods were also chosen based on what audiences would be most familiar with (Frequentist approaches). Bayesian multi-level models are also a choice, but audiences are not as familiar with them and they can be sensitive to priors. as well as
- Because the study was stopped due to practice changes, interpreting results from an early stopped trial can be complex due to potential bias.
- The RCT power calculation is not valid when adding observational data to “boost” sample size, because the assumptions behind RCT power calculations (particularly randomization and control over selection) do not apply to non-randomized data.
- Here is an example of a study using the same methods: Varges D, Manthey H, Heinemann U, et al Doxycycline in early CJD: a double-blinded randomised phase II and observational study *Journal of Neurology, Neurosurgery & Psychiatry* 2017;88:119-125.

Methodology implementation notes

- Six patients were missing hernia size; mesh size was used as a proxy in those cases. While not ideal, this approach maximizes the use of available data.

Additional comments

- The RCT was stopped due to practice changes, which can introduce bias. Early-stopped trials may overestimate the treatment effect or otherwise affect the interpretability of results.
- With a relatively small sample size and potential imbalance in covariates, randomization alone might not ensure balance (even if p-values are > 0.05). Hence, adjusting for known confounders is critical.
- Be wary of exaggerated findings, as smaller studies are more prone to exaggeration.
 - Known as a Type M (magnitude) error. In other words, a finding must be large enough to exceed the statistical significance threshold despite wide confidence intervals, which systematically inflates the estimated effect size. Consequently, although we observed a strong effect, its true magnitude may be substantially lower than our point estimate suggests.[1]

References

[figure not shown]
Gelman, A., & Carlin, J. (2014). Beyond Power Calculations: Assessing Type S (Sign) and Type M (Magnitude) Errors. *Perspectives on Psychological Science*, 9(6), 641-651. <https://doi.org/10.1177/1745691614551642>

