In the MICSIB study by Butler *et al*, all patients received non-cross-linked acellular porcine dermal matrix bioprosthetic mesh. There are several retrospective studies comparing various types of allogenic and xenogenic bioprosthetic meshes in abdominal wall reconstruction. Non-cross-linked porcine mesh has been shown to be superior to human acellular dermis, resulting in fewer instances of laxity/bulge. Non-cross-linked porcine acellular dermis has also been shown to be superior to cross-linked porcine acellular dermis. Non-cross-linked acellular porcine dermal matrix has been shown to result in successful hernia repair in 80% of patients with contaminated or

infected hernias in a retrospective review. Janfaza *et al* retrospectively compared SurgiMend, a non-cross-linked bovine acellular dermal matrix, to Flex HD, a non-cross-linked human acellular dermal matrix. They found higher rates of surgical site infections and hernia recurrence with Flex HD. Clemens *et al* conducted a prospectively collected, retrospectively analyzed study in which they compared hernia repair with Strattice, a non-cross-linked porcine acellular dermal matrix, and with SurgiMend, in 120 patients with mean follow-up of 21.0 months. They found no difference in the rate of recurrent hernia or bulge, although the Strattice group had a higher rate of overall complications due to a relatively higher rate of medical complications (pneumonia, renal failure) in that group not directly related to the type of mesh used.

At the Ohio State University Wexner Medical Center, the two most commonly used biologic meshes for hernia repair in the practice of the senior author ([name]) are Strattice and XenMatrix. These are both non-cross-linked porcine acellular dermal matrices, manufactured by different companies using different technologies. There are some structural differences between the two. For example, according to internal reports by the companies, XenMatrix has larger pores that allows more tissue ingrowth. However, there are no published reports comparing the performance profile those two meshes in the clinical setting.

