## II. Objectives

Our goals in this study are:

- a. PRIMARY OUTCOME
  - i. To compare the **hernia recurrence rate** between XenMatrix and Strattice at **30 days and 1 year postoperatively**
- b. SECONDARY OUTCOMES
  - i. To compare the **bulge rate** between XenMatrix and Strattice at **30 days and 1 year postoperatively**
  - ii. To compare the **rate of Surgical Site Occurrences (SSOs)** between two non-cross-linked porcine dermal matrices (XenMatrix and Strattice) in abdominal wall reconstruction at **30 days and 1 year postoperatively**
    1. Infection
    2. Seroma
    3. Hematoma
    4. Wound dehiscence
    5. Skin necrosis
    6. Formation of enterocutaneous fistula
    7. Mesh infection
  - iii. To compare to changes in patient pain, physical functioning and quality of life after hernia repair between XenMatrix and Strattice, **preoperatively, and at 1 year postoperatively**
    1. **Pain** assessment: PROMIS Pain Intensity survey, PROMIS Pain Interference survey

2. **Physical functioning** assessment: PROMIS Physical Function
3. **Quality of life** assessment: HerQLes survey

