##### Sample size (power analysis)

Our primary outcome is hernia recurrence rate at 30 days and 1 year postoperatively.

According to two industry-sponsored studies, the rate of hernia recurrence with XenMatrix is approximately 7%.

According to the large series by Clemens *et al*, the rate of hernia recurrence with Strattec is approximately 2.9%.

Assuming an alpha error of 5%, a power of 80%, and assuming a large standard deviation (3), the number of patients in each group that is needed to demonstrate a significant difference is 5.

In order to adequately power the study to analyze the secondary outcomes, **we plan to enroll 35 patients in each group (70 patients total)**

*a. Detailed study procedures*

When a patient with a ventral hernia or an abdominal wall tumor presents to the senior author for evaluation for abdominal wall reconstruction, a full history and physical examination will be performed. Patient who satisfy the study inclusion and exclusion criteria will be offered the opportunity to participate in the study. If they agree to participate, informed consent and HIPAA forms will be filled out and signed.

Patients will then be randomized to group A (Strattice) or group B (XenMatrix) using a random number generator made in Microsoft Excel. They will not be told which group they are in, and only the principal investigator, co-investigators and operating room staff will be aware of which mesh is being used.

The patients will be asked to fill out 4 surveys preoperatively: PROMIS Pain Intensity survey, PROMIS Pain Interference survey, PROMIS physical function survey and HerQLes survey.

They will then undergo surgery, and will be followed weekly for a month, then every 3 months for a year, and as needed. They will be evaluated for hernia recurrence, bulge, or other SSOs throughout the follow-up period.

They will be asked to fill out the PROMIS Pain Intensity survey, PROMIS Pain Interference survey, PROMIS physical function survey and HerQLes survey at 1 year.

*c. Measurements*

*The patient characteristics that will be collected will include:*

- 1) Age
- 2) Comorbidities
  - a. Diabetes
    - i. Hemoglobin A1c
  - b. Current tobacco use (defined as <4 weeks prior to surgery)
  - c. Former tobacco use (defined as >4 weeks prior to surgery)
  - d. Chronic Obstructive Pulmonary Disease
  - e. Coronary Artery Disease
  - f. Malnutrition (defined as prealbumin < 18 or albumin < 3.5)
  - g. Corticosteroid use

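### The SAP makes SSO within six weeks its primary outcome without declaring a departure from the protocol's recurrence primary, and it reports no 1-year outcome

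*SAP*

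**What the plan says.** Protocol, Sample size: "Our primary outcome is hernia recurrence rate at 30 days and 1 year postoperatively". Section II (Objectives) gives the same primary. It lists bulge and SSOs as secondary outcomes at the same two times, and a further secondary aim: "To compare to changes in patient pain, physical functioning and quality of life after hernia repair between XenMatrix and Strattice", measured before surgery and at 1 year.

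Protocol, Detailed study procedures: patients "will be followed weekly for a month, then every 3 months for a year, and as needed". On outcomes: "They will be evaluated for hernia recurrence, bulge, or other SSOs throughout the follow-up period". Patients also complete the two PROMIS pain surveys and the "PROMIS physical function survey and HerQLes survey at 1 year".

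Protocol, Data analysis: multivariable logistic regression is planned for recurrence, bulge and SSOs, and for deciding whether one mesh has more complications.

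SAP, Overview: the aim is to evaluate "the effect of using XenMatrix or Strattice mesh on the occurrence of surgical site occurrences (SSO) within six weeks post-surgery". That outcome is modelled under Primary Outcome Analysis in the randomised and observational cohorts separately, and the two estimates are then pooled. Choice of Statistical Methods says that other outcomes have too few events to analyse. The only outcome tables, 3a and 3b, are six-week tables. The Executive Summary calls the adjusted pooled odds ratio statistically significant.

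**The concern.** A protocol secondary, with a window that the protocol does not contain, stands where the protocol primary should be, and the SAP does not mention the substitution. The one SAP supplied is dated February 2025 and already holds the results. A reader therefore cannot tell whether outcome and window were fixed before the data were known.

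Two things are at stake. The 1-year half of the trial's own primary question is not answered in this SAP. And a significance claim is attached to an outcome whose rank and window were not prespecified. The SAP's cautions about early stopping and Type M error do not address a change of outcome.

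**Working it through.** **1. The documents side by side.**

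| Item | Protocol | SAP |
|---|---|---|
| Primary | Recurrence, 30 days and 1 year | SSO, 6 weeks |
| SSO | Secondary, 30 days and 1 year | Primary, 6 weeks only |
| Mesh comparison | Multivariable logistic regression | Simple and multivariable logistic regression per cohort, then REML pooling |
| Recurrence, bulge | 30 days and 1 year | 6-week counts only |
| PROMIS, HerQLes | Before surgery and 1 year | Nothing reported |

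Scheduled visits are weekly to one month and then three-monthly. Days 31 to 42 therefore contain no scheduled visit and rely on as-needed contact.

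**2. The SAP's own figures reproduce.** Randomised SSO (Table 3a) is 11/30 XenMatrix versus 1/16 Strattice.
- Pearson chi-square = 46 × (11×15 − 19×1)² / (30×16×12×34) = 5.01, p = 0.025 (SAP 5.01, 0.03).
- OR = (11×15)/(19×1) = 8.684. SE of the log OR = √(1/11 + 1/19 + 1/1 + 1/15) = 1.100, Wald p = 0.049 (SAP 0.049).
- Observational 4/8 versus 4/12: OR 2.000, SE 0.935.
- REML pooling (tau² = 0.035): OR 3.718 (0.897 to 15.404), p = 0.070, as in the SAP.

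The adjusted pooled OR of 12.476 cannot be re-derived from counts; it needs patient data.

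**3. The 30-day half.** Table 3a gives recurrence of 0/16 and 0/30 by six weeks, so none was recorded by 30 days. The exact upper 95% limit for zero events is 1 − 0.025^(1/n): 20.6% for n = 16 and 11.6% for n = 30. Table 1a shows a minimum follow-up of 0 days for XenMatrix, so 30 need not be the number assessed.

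**4. How many were followed to 1 year (Table 1a, days to last follow-up).**
- Strattice, n = 16: the lower quartile, 727.67, lies between the 4th and 5th ordered values, so at least 12 exceed 365 days. The minimum is 76, so at most 15 do.
- XenMatrix, n = 30: the median, 544, lies between the 15th and 16th values, so at least 15 exceed 365 days. The lower quartile, 140.92, lies between the 7th and 8th, so at least 7 do not, and at most 23 do.

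A last follow-up date is not proof of a hernia assessment.

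**5. What a restored 1-year primary could show.** With zero events, the upper limits would be:
- 12 Strattice patients: 1 − 0.025^(1/12) = 26.5%; 15 patients: 21.8%.
- 15 XenMatrix patients: 21.8%; 23 patients: 1 − 0.025^(1/23) = 14.8%.

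Any recurrence changes these limits. For expected counts, the protocol says "the rate of hernia recurrence with XenMatrix is approximately 7" per cent and gives 2.9% for Strattice, with no time horizon. The series cited for 2.9% compared meshes "in 120 patients with mean follow-up of 21.0 months". If both are assumed to be 1-year rates:
- all 46 assessed: 16×0.029 + 30×0.07 = 2.6 recurrences;
- 12 and 15 assessed: 12×0.029 + 15×0.07 = 1.4.

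Exact power for 16 versus 30 at two-sided 5% is 0.2% (Fisher) or 1.2% (Pearson).

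**6. Sensitivity to the window (hypothetical; no event days are given).**

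| Randomised SSO by day 30 | Fisher p | Pearson p |
|---|---|---|
| 11/30 vs 1/16 (as reported at 6 weeks) | 0.035 | 0.025 |
| 10/30 vs 1/16 (one XenMatrix event after day 30) | 0.068 | 0.040 |
| 11/30 vs 0/16 (the Strattice event after day 30) | 0.008 | 0.005 |

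One event can move the unadjusted randomised result either way. This does not measure the effect of changing the outcome and says nothing about the adjusted OR.

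**The case against.** Much can be said for the SAP. The protocol planned a logistic comparison of the meshes on SSOs and justified 35 patients per group by the secondary outcomes, so comparing SSOs is not itself post hoc. Recurrence is tabulated at six weeks, which settles the recorded 30-day count in the trial. The Overview describes a combined randomised and observational study, and the title block carries a second title, so the word primary may refer to that study. A reason of sorts is offered, namely too few events for other outcomes. The SAP also warns readers about early stopping and exaggerated effects.

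The first two points stand, and they narrow the criticism to rank, window, pooling and the 1-year gap. The third explains the label but not the silence, because the file carries the trial's own title and registration number. The fourth is supported only by six-week counts and does not name recurrence or state a change. It concerns event outcomes, so the missing PROMIS and HerQLes results are simply not reported.

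A reader might go further and infer that SSO was promoted because it reached p = 0.03 while recurrence had no events, that six weeks was chosen to secure significance, or that 1-year data were withheld. The documents support none of these. They do not show when or why the choice was made, they give no event days, and they do not establish that 1-year hernia assessments or survey scores exist. Nor can it be said that 1-year results are unreported everywhere, only that they are absent from this SAP.

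**Conclusion.** The point holds on the text of the two documents and needs correction before the SAP's conclusion is relied on. The SAP's primary differs from the protocol's in outcome and window, and no change is declared. The primary rank, the six-week window and the pooled estimate are not prespecified; the SSO comparison as such is. The 30-day recurrence count is effectively known (none recorded among randomised patients), and the real omission is 1 year.

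The pooled adjusted OR should therefore be read as exploratory. That judgement does not depend on the window scenarios.

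Restoring the primary will not yield a test. Even with no recurrence, the 1-year upper limits would be about 22% to 27% for Strattice and 15% to 22% for XenMatrix, if all patients with last follow-up beyond 365 days were assessed. That range rests on reading the Table 1a quartiles as lying between adjacent ordered values.

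**What to change.** 1. In the SAP Overview and Primary Outcome Analysis, state that the protocol primary was recurrence at 30 days and 1 year. Say when, why and with what knowledge of the data the outcome and window were changed.
2. Report recurrence in randomised patients as the primary. At 30 days, state the zero counts implied by Table 3a, with the number followed that far. At 1 year, give events and numbers assessed by arm with exact binomial intervals among those assessed, or state that no 1-year assessments exist. Present this as an estimate, not a test. Add a time-to-event summary for the unequal follow-up only if events occurred, since the usual Kaplan-Meier variance is zero without them.
3. Report SSO at 30 days and 1 year as the protocol secondary, and bulge likewise. Support the statement about too few events with 1-year counts.
4. Label the primary ranking of six-week SSO, its window and the pooled estimate as not prespecified and exploratory. Qualify the significance statements in the Executive Summary accordingly, beside the existing Type M note.
5. Report 1-year PROMIS and HerQLes scores adjusted for baseline, with the number of patients having both scores, or state that they were not collected.

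The cost is SAP text and a modest reanalysis of outcomes that the protocol planned to collect, with no new patients. The headline SSO result becomes exploratory, and the restored primary will have a wide interval.

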SSO within 6 weeks : Yes	20	4/12 (33.33)	4/8 (50.00)	$\chi^2_1=0.56, P=0.46^2$
SSO Type (cata)				
Skin necrosis : Yes	20	0/12 (0.00)	1/8 (12.50)	$\chi^2_1=1.58, P=0.21^2$
Enterocutaneous fistula : Yes	20	2/12 (16.67)	0/8 (0.00)	$\chi^2_1=1.48, P=0.22^2$

Table 3b: 6-week outcomes, observational patients (*continued*)

Variables	N	Strattice	XenMatrix	Test Statistic
Dehiscence : Yes	20	2/12 (16.67)	0/8 (0.00)	$\chi^2_1=1.48$, P=0.22 ²
Seroma : Yes	20	1/12 (8.33)	0/8 (0.00)	$\chi^2_1=0.70$, P=0.40 ²
Hematoma : Yes	20	0/12 (0.00)	0/8 (0.00)	NA
Infection : Yes	20	1/12 (8.33)	3/8 (37.50)	$\chi^2_1=2.55$, P=0.11 ²
Mesh infection : Yes	19	0/11 (0.00)	0/8 (0.00)	NA

Note:

N is the number of non-missing value. 1 Kruskal-Wallis. 2 Pearson. 3 Wilcoxon.

Stat, P is the test statistic and p-value.

cata = check all that apply

Results

Executive Summary

Unadjusted Random Effects Meta-Analysis (Simple Logistic Regression):

Effect Estimate (Odds Ratio): 3.718 (0.897, 15.404)

Significance: The pooled estimate was not statistically significant.

Heterogeneity:

I^2 (total heterogeneity / total variability): 3.29%

H^2 (total variability / sampling variability): 1.03

Test for Heterogeneity:

$Q(df = 1) = 1.0340$, $p\text{-val} = 0.3092$

There appears to be minimal variability between the two studies. The I^2 value of 3.29% indicates that nearly all of the total variation can be explained by chance rather than true heterogeneity, and an H^2 of 1.03 reflects low excess variability. The Q test ($Q = 1.034$, $p = 0.3092$) is nonsignificant, confirming that there is no strong evidence of meaningful heterogeneity.

Adjusted Random Effects Meta-Analysis (Multivariable Logistic Regression):

Effect Estimate (Odds Ratio): 12.476 (1.745, 89.199)

Significance: The pooled estimate was statistically significant.

Heterogeneity:

I^2 (total heterogeneity / total variability): 0.00%

H^2 (total variability / sampling variability): 1.00

Test for Heterogeneity: $Q(df = 1) = 0.2830$, $p\text{-val} = 0.5947$

There is effectively no evidence of meaningful heterogeneity between the RCT and the observational study, provided by 0.00% I^2 value. Similarly, $H^2 = 1.00$ supports the absence of excess variability beyond what would be expected by sampling error alone. Finally, the Q test ($Q = 0.2830$, $p = 0.5947$) is non-significant, confirming that the studies are consistent and do not exhibit statistically detectable heterogeneity.

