When covariates were included in the model, a previously non-significant association between the exposure and outcome became statistically significant. This shift suggests that the unadjusted analysis may have been confounded—i.e., certain variables were masking or biasing the relationship.

Note

Be wary of exaggerated findings, as smaller studies are more prone to exaggeration. This is known as a Type M (magnitude) error. In other words, a finding must be large enough to exceed the statistical significance threshold despite wide confidence intervals, which systematically inflates the estimated effect size. Consequently, although we observed a strong effect, its true magnitude may be substantially lower than our point estimate suggests.

Gelman, A., & Carlin, J. (2014). Beyond Power Calculations: Assessing Type S (Sign) and Type M (Magnitude) Errors. *Perspectives on Psychological Science*, 9(6), 641-651.

[figure not shown]
Random Effects Meta-Analysis: Simple Logistic Regression

Simple logistic regression = logistic regression with no adjustment for confounders

[figure not shown]
Random Effects Meta-Analysis: Simple Logistic Regression

Study	Estimate (log OR)	95% CI (log OR)	Estimate (OR)	95% CI (OR)	P-value
Randomized	2.162	(0.365, 5.123)	8.684	(1.441, 167.853)	0.049
Observational	0.693	(-1.143, 2.597)	2.000	(0.319, 13.423)	0.459
RE Meta-Analysis	1.313	(-0.108, 2.735)	3.718	(0.897, 15.404)	0.070

Forest Plot: Log Odds Scale

Forest Plot: Odds Scale

[figure not shown]

Random Effects Meta-Analysis: Multivariable logistic regression

[figure not shown]
Random Effects Meta-Analysis: Multivariable Logistic Regression

Study	Estimate (log OR)	95% CI (log OR)	Estimate (OR)	95% CI (OR)	P-value
Randomized	2.968	(0.815, 6.261)	19.458	(2.258, 523.717)	0.023
Observational	1.882	(-0.898, 5.783)	6.569	(0.407, 324.629)	0.230
RE Meta-Analysis	2.524	(0.557, 4.491)	12.476	(1.745, 89.199)	0.012

Log Odds Scale

Odds Scale

FAQ

Q: What is overfitting?

A: Overfitting in regression happens when a model is too complex, often due to too many parameters relative to a small sample size, causing it to capture noise rather than the true data pattern. With limited data, the model lacks sufficient information to generalize well, leading to poor performance on new data because it is overly tailored to the specific quirks of the training set.

Q: What is a chunk (or composite) test?

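### The SAP aims at the effect on SSO risk but gives only odds ratios as effect measures; risk differences should be added and the rise in the adjusted OR should not be read as confounding

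*SAP*

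**What the plan says.** The Overview gives the purpose of combining the randomised trial and the observational cohort as "to generate an overall estimate of the treatment effect of mesh type on the risk of SSO". The protocol's Objectives likewise ask for a comparison of the rate of SSOs between the two meshes.

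The SAP section Primary Outcome Analysis sets the effect measure: "A combined estimate for the log odds ratio was calculated using inverse variance weighting and a restricted maximum likelihood estimator". On output it adds: "Forest plots and summary tables for the log odds ratio and odds ratio were generated to summarize results". For the multivariable fits, "Both models were adjusted by hernia width, CDC wound class, immunosuppression, and recurrent hernia".

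The Executive Summary reports the unadjusted result as "Effect Estimate (Odds Ratio): 3.718 (0.897, 15.404"), not significant, and the adjusted result as "Effect Estimate (Odds Ratio): 12.476 (1.745, 89.199"), significant. It then says that the shift suggests the unadjusted analysis may have been confounded. The Note that follows warns that "although we observed a strong effect, its true magnitude may be substantially lower than our point estimate suggests"; its stated reason is small samples (Type M error), not the odds-ratio scale.

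Tables 3a and 3b print SSO counts and percentages by arm. Neither the SAP's methods nor its results give a risk difference or risk ratio with an interval.

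**The concern.** A surgeon choosing a mesh needs the SSO risk with each product and the difference between them, with its uncertainty. When about 30% of patients have the event, and 50% in one arm, an odds ratio answers a different question and is easily misread as a ratio of risks. The SAP's own FAQ on large p-values shows how to describe complication rates with an interval in percentage points, but the results supply no such interval.

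The second issue is interpretation. A logistic odds ratio adjusted for covariates is conditional on them. It can move away from 1 when prognostic covariates enter, even with no confounding, and it can be inflated when events are few relative to model terms. Presenting the move from 3.7 to 12.5 as a sign of confounding lends the larger figure an authority that the data printed in the SAP do not establish.

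**Working it through.** **Inputs** (SAP Tables 3a and 3b, SSO within 6 weeks, XenMatrix v Strattice)
- Randomised: 11/30 (36.7%) v 1/16 (6.25%).
- Observational: 4/8 (50.0%) v 4/12 (33.3%).
- Incidence: 12/46 = 26.1%, 8/20 = 40.0%, together 20/66 = 30.3%.

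**1. Reproduce the SAP's pooled odds ratios** (inverse variance, REML)
- Unadjusted log ORs: ln[(11×15)/(19×1)] = 2.162 and ln[(4×8)/(4×4)] = 0.693.
- Variances: 1/11 + 1/19 + 1/1 + 1/15 = 1.210 and 1/4 + 1/4 + 1/4 + 1/8 = 0.875.
- With τ² = 0.0354 the weights 1/(v + τ²) are 0.803 and 1.098. Pooled log OR = (0.803×2.162 + 1.098×0.693)/1.901 = 1.313, SE 0.725. OR = 3.718 (0.897 to 15.404), Q = 1.034, I² = 3.29%, p = 0.070. This matches the SAP.
- Adjusted: the stated log ORs 2.968 and 1.882, with SEs back-calculated from the stated p-values (1.306 and 1.568), give 12.47 (1.745 to 89.09), p = 0.012. This matches within rounding of the p-values.

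**2. Risk differences by source** (Newcombe intervals)
- Randomised: 36.7 − 6.25 = 30.4 points (3.8 to 49.0).
- Observational: 50.0 − 33.3 = 16.7 points (−23.0 to 51.2).

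**3. Pool the same unadjusted data on the risk scales**
- REML risk difference: variances 0.01140 and 0.04977, τ² = 0. (87.70×0.3042 + 20.09×0.1667)/107.79 = 0.279, SE 0.096: 27.9 points (9.0 to 46.7).
- Mantel-Haenszel risk difference: weights 30×16/46 = 10.43 and 8×12/20 = 4.80. (10.43×0.3042 + 4.80×0.1667)/15.23 = 0.261: 26.1 points (6.2 to 46.0).
- REML risk ratio: log RRs 1.769 and 0.405, τ² = 0.287. RR = 2.29 (0.67 to 7.90).
- Mantel-Haenszel risk ratio: (11×16/46 + 4×12/20)/(1×30/46 + 4×8/20) = 6.226/2.252 = 2.76 (1.02 to 7.47).

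The position relative to the null is therefore not stable. The REML OR and REML RR intervals include 1. The Mantel-Haenszel RR and both risk-difference intervals exclude the null.

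**4. What an OR of 12.476 means at given reference risks**

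RR = OR/(1 − p₀ + p₀×OR):
- p₀ = 6.25% (randomised Strattice): RR 7.3.
- p₀ = 5/28 = 17.9% (all Strattice): RR 4.1.
- p₀ = 33.3% (observational Strattice): RR 2.6.

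None is near 12. At the last two risks the largest possible RR, 1/p₀, is 5.6 and 3.0. These conversions show only that the OR is not a relative risk. Because 12.476 is conditional on covariates and these risks are crude, they do not estimate the adjusted RR.

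**5. How much of the distance from 12.5 to the unadjusted RR is scale?**
- Against the Mantel-Haenszel RR: ln(12.476/2.76) = 1.51. Adjustment accounts for ln(12.476/3.718) = 1.21 (about 80%), and OR-to-RR for ln(3.718/2.76) = 0.30 (about 20%).
- Against the REML RR: ln(12.476/2.29) = 1.69, of which 1.21 is about 71%.

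**6. Can the adjustment step be attributed to confounding?**
- The randomised OR itself moved from 8.684 to 19.458, a factor of 2.24, although randomisation leaves only chance imbalance to confound it.
- Mesh plus four covariates is at least five slope terms. With 12 and 8 events that is at most 12/5 = 2.4 and 8/5 = 1.6 events per term.
- Confounding or chance imbalance, non-collapsibility and sparse-data bias are all possible. The printed tables cannot separate them.

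**7. Illustration only**

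Assume a normally distributed covariate effect on the log-odds scale with SD 0 to 3, calibrated to 30.3% incidence. A conditional OR of 12.476 then implies a marginal RR from about 7.0 down to 2.4 and a risk difference from about 41 down to 24 points. The SD is an assumption; the documents do not give it.

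**The case against.** The strongest defence is that odds ratios follow from the plan. The protocol's Data analysis section prescribes binary logistic regression to judge whether one mesh has a higher complication rate, and the SAP names the log odds ratio openly. It labels every estimate as an odds ratio, never claims twelve times the risk, prints the arm percentages, and warns twice that the true effect may be much smaller. All of that stands. It makes this a gap in reporting and interpretation, not an error in a fitted number. The magnitude warnings rest on sample size, however, and do not cover the scale of the measure.

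A reader might infer that 12.5 is an inflated version of a risk ratio of 2.8 and a difference of 26 points. The documents do not support that: it sets an adjusted conditional OR against unadjusted risk measures, and most of the gap is covariate adjustment (step 5). A reader might also apply 12.476 to the pooled Strattice risk of 17.9%, obtain 73% on XenMatrix, and hold that against the observed 15/38 = 39.5%. That combines a conditional OR with a crude risk, and crude counts cannot contradict an adjusted estimate. Nor is it shown that adjustment would matter much less on the risk scale; that depends on covariate-outcome links that are not printed.

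A further objection is that changing the effect measure or estimator once results are known could move the unadjusted result across the null. Step 3 confirms this, so the risk measures should be additions, labelled post hoc, and not replacements.

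**Conclusion.** The point holds as a gap between the stated target and what is reported. The SAP aims at risk, SSO is common, and no risk difference or risk ratio with an interval is given. Unadjusted, the pooled OR of 3.72 goes with a risk ratio of 2.29 (REML) to 2.76 (Mantel-Haenszel) and a risk difference of 26.1 to 27.9 points; these rest on the printed counts and on pooling the two sources as the SAP does. The adjusted risk ratio and difference need patient-level data, so no adjusted figure is offered here. Confounding is one possible explanation of the larger adjusted OR, but the shift is not evidence for it. Confidence is high on the missing measures and the unadjusted figures. How far the adjusted OR departs from its risk-scale counterpart remains open.

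**What to change.** Keep the odds ratios and the stated REML pooling. In Primary Outcome Analysis and the Executive Summary:

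- Add the SSO risk in each arm and the difference with its Newcombe interval for each source, using the figures in step 2.
- Add the pooled risk difference by the SAP's own REML method, 27.9 points (9.0 to 46.7), with the Mantel-Haenszel value of 26.1 (6.2 to 46.0) as a check.
- Add risks standardised from each fitted adjusted model, with their difference. Use bootstrap or penalised-fit intervals because events are few, and state how the two standardised differences are combined.
- Label these measures post hoc, make no new significance claim from them, and state that the conclusion about the null depends on scale and estimator.
- Reword the Executive Summary passage on the shift between models: the conditional OR moved away from 1 on adjustment, which may reflect confounding or chance imbalance, non-collapsibility or sparse-data bias, and the data do not distinguish these.

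The cost is a modest extra analysis of data already held, some added text, and a less dramatic headline. Standardisation will not cure sparse-data bias in the underlying fits, and the text should say so.
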